15 REFERENCES

30

Revision History

Version Number	Description of Change	Effective Date
Version 1	Initial release	20 Mar 2017
Version 2		13 Feb 2018
Version 3		13 Aug 2019
Version 4		07 Oct 2021
Version 5-R		02-Mar 2022
Version 6-R		02-May-2022
Version A		01-Jun-2022

List of abbreviations

Abbreviation	Definition
ADE	Adverse device event
AE	Adverse event
CIR	Company-in-residence [REDACTED]
CRF	Case report form
FDA	Food and Drug Administration (United States)
[REDACTED]	[REDACTED]
GCP	Good clinical practices
ICF	Informed consent form
IFU	Instructions for use (User manual)
IRB	Institutional review board
NADPH	Reduced nicotinamide adenine dinucleotide phosphate
PHI	Protected Health Information
SADE	Serious adverse device event
SAE	Serious adverse event
UADE	Unanticipated adverse device effect
US	United States

Study summary

Title	Nonlinear imaging of skin in vivo
Protocol number	[REDACTED]
Phase	Feasibility
Methodology	Single center, open label, one-arm observational study
Study duration	Up to 5 years
Study center(s)	Single-Center, [REDACTED]
Objectives	
The overall objective of this study is to investigate the potential for the Vio™ to display microscopic skin structure in people of different age, sex, race, and skin health.

Aims	
Aim 1: Quantify imaging performance in various types of skin, which may include estimated in vivo resolution and imaging depth. Various types of skin includes skin of different people as well as skin in different locations on the body, and skin with skin disease, including basal cell carcinoma
 
Aim 2: Qualitatively evaluate image quality and interpretability by physicians trained in dermatopathology as a function of skin type.
 
Because this study is purely observational, there are no established quantitative endpoints.

Number of subjects	Up to 120 subjects
Inclusion Criteria	
Subjects, ages 2 – 90 years old.
 
Subject, or guardian, if applicable, must be willing to provide written informed consent prior to enrollment and agree to comply with protocol requirements. If applicable, child must be willing to provide written assent prior to enrollment and agree to comply with protocol requirements.

Study summary

Subject or guardian, if applicable, must have sufficient mental capacity to understand the Informed Consent and provide clinically relevant and reliable feedback regarding their experience with the device.

Subject and guardian, if applicable, must comply with the protocol requirements.

Subject or guardian, if applicable, must agree that anonymized personal data will be made available to Study Sponsor and requisite regional and international regulatory bodies.

Exclusion Criteria

Any general health condition or systemic disease that may represent, in the opinion of the Principal Investigator, a potential increased risk associated with device use

Currently infected with a communicable skin infection (e.g., shingles or methicillin-resistant S. aureus), which does not include local and minimally pathogenic or non-pathogenic infections distant from the imaging location(s) (e.g., warts, acne)

Any known allergies to any materials used in the preparation of skin and/or device use

Has a temporary or permanent electrical implanted medical device

Study product

VioTM system – nonlinear microscopy imaging system; blunt, non-invasive, low-power infrared light, without exogenous dye

Duration of subject's participation

One visit up to multiple visits; typically 1 hour per visit, no more than 3 hours per visit. Subjects will be monetarily compensated up to \$100 per visit.

1 Introduction

1.1 *Background*

Cellular pathology has long provided a powerful means to identify diseases of solid tissues. The emergence of the microscope as the centerpiece of pathology transformed our understanding and diagnosis of cell-based disease, from neoplasia to infarction to infectious disease.¹ In particular, our understanding of cancer has been heavily influenced by surgical pathology since the emergence of anesthesia and aseptic technique in the late 1800s.²

Basal cell carcinoma and squamous cell carcinoma, the most common forms of cancer, as well as melanoma occur in the skin and are diagnosed using invasive biopsies paired with cellular pathology. Many other non-malignant skin diseases, such as fungal infection, are also confirmed with cellular pathology. These pathologies occur in the top layers of skin, less than 0.5 mm below the surface. Biopsies for malignancies of the skin are ultimately found to be benign over 70% of the time³, which means that, each year, patients with ultimately healthy skin experience the risk, inconvenience, and, possibly, anxiety of over 13 million invasive biopsies every year⁴. As such, the ability to visualize skin cellular anatomy noninvasively represents an important unmet medical need.

No clinically-feasible imaging system allows for noninvasive access to skin cellular anatomy. For the past two decades, second harmonic generation and two-photon autofluorescence, collectively called nonlinear imaging, have been used to image skin⁵. These nonlinear imaging systems, however, are too bulky, slow, and expensive for clinical feasibility. Recently, the invention of extreme miniaturization of nonlinear imaging systems has opened up the possibility of bringing this powerful technology to the clinic⁶.

The investigation of a noninvasive, nonlinear microscope to image healthy human skin will allow for the characterization of the imaging performance of this important new technology in a variety of skin types. The ability to visualize cellular architecture of skin without gathering a destructive biopsy may pave the way for rapid, noninvasive surgical pathology in the future both in skin and throughout the body.

1.2 *Investigational device: VioTM*

Enspectra Health has developed a noninvasive and real-time imaging technique that makes it possible to provide histology-like images of epithelial tissue with subcellular resolution and dye-free color contrast.

The technique uses the intrinsic signals from second harmonic generation created by collagen and two-photon autofluorescence created by cytoplasmic molecules; thus, imaging is performed without exogenous dyes.

Our system consists of 2 primary components: **(1) an imaging hub**, which contains the near infrared pulsed light source, the control electronics, the optical sensors, and a monitor, which may be optionally placed on a wheeled cart, **(2) a handheld imaging wand**, which is tethered to the hub by fiber optic and electrical cables and held by the user, and includes a cleanable imaging probe,

which directly contacts patient skin-of-interest (Fig. 1).

1.3 Clinical data to date

Two-photon fluorescence microscopy has been used to image human skin *in vivo* for nearly two decades⁵, although not in a portable format. Spectroscopic data suggest that reduced nicotinamide adenine dinucleotide phosphate [NADPH] is the primary source of two-photon autofluorescence

with a 730 nm excitation source. NADPH is primarily found in cellular cytoplasm outside of the nucleus, resulting in images of cells that reveal cellular shape and size⁵ and an absence of signal from the nucleus which may suggest nuclear shape and size as well.

Both two-photon microscopy and second harmonic generation imaging can be performed simultaneously to create a multi-color image with just a single laser light source because the wavelengths of the resulting light from two-photon autofluorescence and second harmonic generation are spectrally separated. When both modalities are combined to image skin, second harmonic generation microscopy provides a view of the connective tissue-rich dermal layer, which is primarily composed of collagen, while two-photon fluorescence microscopy provides of view of cell morphology in the epidermal layer⁷. Nonlinear imaging of skin *in vivo* has been used successfully to identify cellular features characteristic of malignancy by several groups in multiple studies⁸⁻¹⁶.

1.4 Risks and benefits

1.4.1 Benefits

There is no direct health benefit to the participant.

The primary benefit of this study comes from the scientific knowledge gained about the capabilities of nonlinear imaging to display clinically-relevant features of cellular structure and architecture noninvasively. The ability to noninvasively inspect skin cellular structure will deepen our understanding of skin physiology, pathology and enable longitudinal follow up in future studies. Such technology may also hasten the diagnosis of malignancy and other skin pathologies by lowering patient burden (pain, risk of scarring, anxiety) compared to invasive biopsies.

1.4.2 Risks

The risks of this protocol are considered to be no more than minimal. The *VioTM* procedure described in this protocol is similar to a commonly performed clinical procedure: dermoscopy. Like dermoscopy, the *VioTM* procedure involves non-invasive illumination of skin and magnification of skin structures. Dermoscopy is generally considered to be safe; dermoscopy systems are typically classified by the United States Food and Drug Administration as Class I medical devices, except for Visiomed's microDERM, which, unlike *VioTM*, involves computer-assisted diagnosis and is considered a Class II medical device. Unlike medical devices, *VioTM* will not be used to diagnose or treat disease in this protocol, even though images may be taken of skin with disease.

A systematic review found that, among the 433 abstracts that addressed dermoscopy, “no study systematically assessed harms to either patients or the operators from the use of dermascope.” Two case reports described possible harm due to dermoscopy: (1) dermoscopy immersion oil contaminated with cedarwood oil was reported to have caused allergic contact dermatitis in one patient, and (2) intensive use of dermoscopy may have caused tonic pupil (Adie’s pupil) in a dermatologist¹⁷. We will limit the risk of allergic contact dermatitis by using an immersion fluid approved to be used in medical settings (e.g., pharmaceutical-grade mineral oil, antibacterial alcohol gel, ultrasound gel). Additionally, the *VioTM* device comprises materials generally considered biocompatible when used in similar devices for similar applications (e.g., 316L steel,

medical-grade silicone). Concerns have also been raised about patient risk for nosocomial infection when contact dermoscopy is used and the dermascope is not fully cleaned between patients, although it should be noted that dermoscopy is typically used to image intact skin¹⁷. We will mitigate the risk of infection in this protocol by cleaning the probe between subjects. We may additionally use a single-patient-use, disposable silicone barrier, which may also diminish infection risk. The user applying excessive pressure during use may cause contusions to the skin at the site of imaging. This risk will be mitigated by instructing the user to avoid applying excessive pressure. *VioTM* imaging and risks vary slightly from those of dermoscopy because the light source used is a near infrared laser instead of white light.

Skin: The *VioTM* takes an image of skin tissue by exciting the tissue with laser light, which could introduce the risk of tissue damage if the light power was above a safety threshold. The *VioTM*, however, uses an ultrafast pulsed laser to maintain an overall low average power level¹⁸ so tissue is not damaged, while still providing the high instantaneous intensities needed for nonlinear imaging. Intensity powers are less than 10 kW/ μm^2 , which are less than powers associated with tissue damage (16 kW/ μm^2)¹⁹.

Eyes: Light from the probe tip diverges rapidly, which decreases light power density as a function of distance from the probe tip (Class 1M laser). The Investigator may not choose to investigate the eyelid to remain consistent with earlier data collection in this protocol. Recent testing of the device reveals no substantial risk to the eyes of the patient or user.

Of note, no adverse events have been reported with the use of nonlinear imaging of skin *in vivo* by other groups⁸⁻¹⁶.

Relevant risk analyses have been conducted in relation to imaging accessible skin surfaces. Deliberate misuse of the device to image tissues not approved on this protocol may introduce additional risks. These tissues and associated risks include but are not limited to the cervix, gastrointestinal tract, and oral cavity (infection because the non-disposable components have not been designed for the more stringent disinfection that would be required between patients); and interior tissues accessed surgically (infection because the device has not been designed to be used in a surgical sterile environment).

Finally, because the device may be used to image skin with known or suspected skin disease, there is a risk that the *VioTM*, a research-use only device, could improperly influence healthcare decisions or be perceived by the subject to be a part of disease diagnosis. To minimize this risk, images gathered with the *VioTM* paired with PHI will not be shared with the subject's physician or the recruiting physician, if applicable. Any physicians involved in recruitment will be specifically trained that the *VioTM* is for research-use only. The ICF will emphasize to the subject that neither the device nor the study impacts disease diagnosis or treatment.

1.4.3 Risk versus benefits

The minor risks associated with this study are outweighed by the scientific knowledge to be gained about a new imaging technology that may decrease the need to invasively biopsy patients in the future.

2 Investigator(s) and other study personnel

Whenever the term 'Investigator' is noted in the protocol text, it may refer to either the Principal Investigator at the site, or an appropriately qualified, trained, and delegated individual of the investigational site.

The study sponsor, termed 'Sponsor', is identified on the title page of this protocol, and also serves as the Sponsor-Investigator. The Sponsor will select qualified Investigators from within the organization, obtain signed study agreements, and provide the Investigators with the information necessary to conduct the study. Training on the *VioTM* procedure will occur.

The Principal Investigator must sign the protocol signature sheet before subject recruitment may start at the respective center. Likewise, all protocol amendments/integrated protocols must be signed and dated by the Principal Investigator before coming into effect at the respective center.

A complete list of all participating centers and their Investigators, as well as all required signature documents, will be maintained in the Sponsor-Investigator study file.

All other study personnel not included in this section are identified in a separate personnel list (not part of this clinical study protocol) as appropriate. This list will be updated as needed.

3 Study objectives

The overall objective of this study is to investigate the potential for the *VioTM* to display microscopic skin structure in people of different age, sex, race, and skin health.

3.1.1 Aim 1

Quantify imaging performance in various types of skin, which may include estimated in vivo resolution and imaging depth. Various types of skin includes skin of different people, skin in different locations on the body, and skin with skin disease, including basal cell carcinoma.

3.1.2 Aim 2

Qualitatively evaluate image quality and interpretability by physicians trained in dermatopathology as a function of skin type.

A large rectangular area of the page has been completely blacked out with a solid black redaction mark, obscuring several paragraphs of text.

The safety of device usage will also be evaluated by monitoring adverse events as described in Section 9.

4 Study design

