4.1 Overview

This is a single-center, open-label, one-arm observational clinical study. Up to 120 subjects will be enrolled in the study. Each subject will participate in one session for a maximum of 3 hours, but typically

lasting an hour, including the preparation and consent process. Subjects will be monitored for AEs during and immediately following the procedure. Subjects will be requested to self-report any AEs for up to seven days following the procedure. The overall study duration is expected to be approximately 5 years

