5.3 Subject recruitment and screening

Subjects will be recruited for the study using advertisements communicated with flyers, pamphlets, classified ads in local newspapers, electronic posts to sites such as Craigslist.com or SUPost.com, emails to listservs, word-of-mouth, and/or physician referral/recruitment. If a subject is recruited by physician, with permission of the possible subject, the physician may optionally mark a region of interest of skin to be investigated to assist the other study staff (e.g., with a small bandage or a small mark with skin marker). This marking process will likely occur before informed consent for the study has been received because the full explanation of the study will be presented in a separate space without the referring physician present. The marking is temporary; informed consent for the study will be conducted within an hour of marking placement.

After the subject provides written informed consent, the subject will be screened by the Investigator or designee using the protocol defined inclusion and exclusion criteria to determine study eligibility.

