7.1.3 Baseline questions

Enrolled subjects will answer questions about demographics, including age, race, ethnicity, and sex, as well as questions about their relevant medical history.

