7.2.3 Image and video collection

We may capture macroscopic images of the subject using a commercially available camera to capture the location and context of the skin to be imaged with the device. We may also image skin using a commercially available dermatoscope to accurately capture skin tone and other macroscopic skin features. Dermatoscope imaging may occur either before or after applying immersion fluid depending on the type of dermatoscope used. Imaging with the *VioTM* will begin after skin preparation. Each *VioTM* image and video requires only a few seconds to acquire. Macroscopic imaging, dermatoscope imaging, and *VioTM* imaging may occur in any order. Participants may volunteer for more than one imaging location (e.g., the cheek, the forearm, the hand) in a single session. Steps 7.2.2 and 7.2.3 may be repeated for different imaging locations.

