8.2 Statistical methods

The primary analysis involves the quantification of imaging performance of the *VioTM* as a function of skin type, location (e.g., forearm, ear, nose), and health of skin. Because group sizes are small, statistical comparisons are unlikely to be significant. Still, data from this study will be important for planning statistically robust future studies. As a secondary aim, image performance will also be qualitatively evaluated by physicians trained in dermatopathology interpretation. Interim analyses are not planned.

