9.3 Randomization codes and unblinding procedures

All enrolled subjects will undergo imaging with the *VioTM*. Subject group, therefore, will not be randomized nor blinded.

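### Does the plan need a rule masking the physicians who read images for Aim 2?

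*Combined protocol and SAP*

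**What the plan says.** Section 3.1.2 and the Study summary state Aim 2 as "Qualitatively evaluate image quality and interpretability by physicians trained in dermatopathology as a function of skin type". Section 8.2 adds, as a secondary aim, that "image performance will also be qualitatively evaluated by physicians trained in dermatopathology interpretation". It gives no reading procedure.

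On design, Section 4.1 says "This is a single-center, open-label, one-arm observational clinical study", and Section 9.3 says "Subject group, therefore, will not be randomized nor blinded". The Study summary adds: "Because this study is purely observational, there are no established quantitative endpoints".

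The study collects information that would tell a reader which group an image belongs to. Section 7.1.3: "Enrolled subjects will answer questions about demographics, including age, race, ethnicity, and sex, as well as questions about their relevant medical history". Section 7.2.3: "We may also image skin using a commercially available dermatoscope to accurately capture skin tone and other macroscopic skin features". Under Section 5.3, where a physician recruits the subject, "the physician may optionally mark a region of interest of skin to be investigated".

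Three further provisions bear on the point. Section 1.4.2 keeps device images linked to PHI away from the subject's own physician and the recruiting physician. Section 10.1 puts only a subject code on the CRF, and Section 10.2 has images and videos stored electronically.

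**The concern.** Aim 2 rests on opinion, and the opinion is to be compared by skin type. A reader who knows the age, race, history or disease status, or who has seen the dermatoscope image, knows the grouping variable. If that reader expects darker, older or diseased skin to image poorly, the expectation can enter the rating, and part of an apparent difference between groups would come from the reader and not the device. The readable text does not withhold this information, set a reading order, or say whether the readers are separate from those who recruit and image the subjects.

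At stake is how far the by-skin-type description can be trusted if it is carried into later work. Section 4.2 expects feasibility data from this study to inform later investigations, although it does not single out Aim 2.

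**Working it through.** No arithmetic settles this. The only planning figure is the 120 in Section 8.1: 2 × 2 × 5 × 5 = 100, leaving 120 − 100 = 20 as overhead. That is a count of demographic and technology cells, with no precision target for the physician readings. A bias calculation would need a rating scale, a spread of ratings and a number of readers, and the readable text gives none of them. The check is therefore a comparison of the relevant sections.

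1. **Do the open-label and no-blinding statements say that readers are unmasked?** No. Section 9.3 gives its reason: every enrolled subject is imaged with the device. With one arm there is no allocation to conceal. Sections 4.1 and 9.3 describe that fact and do not address what a physician sees when reading a stored image.

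2. **Do the privacy rules mask readers?** Only in part, and for another purpose. Subject codes hide identity but not skin type or disease. The PHI rule in Section 1.4.2 is there so that care decisions are not influenced. It does mean that a recruiting physician who also read images could not be given that device image with PHI attached, but such a reader might still recognise a marked lesion.

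3. **Is the reading procedure absent from the plan?** This cannot be established. Several paragraphs are blacked out immediately after the Aim 2 sentence, a natural place for detail on that aim. Text is also lost at the end of Section 6, the numbering passes from 7.4 to 7.6, and Figure 3 is not shown. Reader identity may sit elsewhere too, because Section 2 refers to a separate personnel list outside the protocol.

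4. **Does any readable rule force a wrong result?** No. With coded subjects and electronic files, physicians can be given device images alone, in random order, under the plan as it stands.

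5. **What would a written masking rule gain?** It could withhold demographics, history and companion photographs. It could not withhold what the device image itself shows. Section 1.3 reports that nonlinear imaging has been used to pick out features of malignancy, and pigment or body site may also be visible (an assumption; the documents do not say). Masking would therefore be partial for the very attributes that define the comparison.

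6. **Does reading order matter?** Section 8.1 lists two technology versions and Section 4.1 expects about 5 years of study. If images were read as collected and the versions were used one after the other, growing reader familiarity would run alongside device version. Aim 2 compares skin types, not versions. Skin-type comparisons would be affected only if skin groups were also enrolled or read at different times, and nothing in the documents says so.

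**The case for a change.** The strongest case for a change is that Sections 8.2 and 9.3, both natural homes for a reader rule, show no redaction and are silent. The judgement is subjective, the grouping information is collected, and Section 2 has the sponsor choose investigators from within its own organisation, so independence of the readers cannot be taken for granted. Section 7.3 shows that the authors care about bias, since it keeps data from subjects who stop early for that reason. One sentence in Section 8.2 would cost little, and a later reading with clinical context could still be reported separately.

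Part of this stands. A first reading of coded device images, without history or companion photographs, is good practice, and in that modest form it is cheap. But Section 8.2 is one short paragraph and need not repeat procedures that may be set out under the aims. A fuller rule is not cheap. Holding images until a batch spans skin groups and device versions could delay reading for a long time in a study of about 5 years, and requiring readers who neither recruited nor imaged the subject may mean finding additional physicians. In return, the masking would be incomplete.

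**Conclusion.** No change to the plan follows. In the readable text the reading conditions for Aim 2 are unspecified. That is missing detail at most, and it may be supplied in the redacted paragraphs.

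The consequence is small in kind, though it cannot be given a number. Aim 2 is secondary and qualitative and has no established quantitative endpoint. Section 8.2 already warns that group comparisons are unlikely to be significant, and Section 1.4.2 keeps the device out of diagnosis and treatment. Nor is anything lost for good: the files are stored, so physicians without access to subject information can read or re-read them later if the by-skin-type description proves important.

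This rests on two assumptions: that the stored files can be shown without the companion material, which the coding and storage arrangements in Sections 10.1 and 10.2 suggest, and that Aim 2 is reported as description and not as a tested comparison.
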